2.3 Rationale

A major goal of breast oncologists as well as national and international breast oncology cooperative groups is to decrease late toxicities for patients with curable malignancies. Given the relatively high disease free and overall survival rates for breast cancer, improving functional outcomes by decreasing the long term complications of radiation therapy is a major goal. Many women now undergo reconstruction prior to radiation therapy. Technical limitations of widely available radiation techniques often lead to the need for additional manipulation of the breast reconstruction or even removal of breast reconstruction or implant prior to radiation therapy. This can impact quality of life, and self image for the patient, decrease the chance of a cosmetically acceptable result, and is more costly. The physical properties of protons allow for delivery of radiation without compromise with breast reconstruction in place. Cardiac exposure is still a major concern for patients with unfavorable cardiac anatomy. Given anticipated long term survival for many of these patients and risks of cardiac disease from chemotherapeutic and targeted agents used for care, it is important to decrease exposure to radiation. Protons will decrease cardiac exposure to radiation.

3. PARTICIPANT SELECTION

3.1 Eligibility Criteria

Participants must meet the following criteria on screening examination to be eligible to participate in the study:

- 3.1.1 Participants must have histologically confirmed invasive breast cancer confined to the breast and regional lymphatics (supraclavicular, axillary, internal mammary lymph nodes).
- 3.1.2 Participants must have completed definitive breast surgery (mastectomy or breast-conserving)+/- reconstructive surgery with referral for definitive chest wall radiation therapy. Patients with breast reconstruction are eligible if it determined

CONFIDENTIAL

This document is confidential. Do not disclose or use except as authorized.

by the referring or treating radiation oncologist that plan would be suboptimal without manipulation of breast implants. For patients without reconstruction, they must meet eligibility by having unfavorable cardiac anatomy defined as $\geq 5\%$ of the heart receives ≥ 20 Gy and/or LAD receives ≥ 20 Gy with conventional planning. Participants do not need to have measurable disease. Most patients will not have measurable disease at the time of treatment.

3.1.3 Age ≥ 18 at the time of diagnosis

3.1.4 Life expectancy of greater than 12 months.

3.1.5 ECOG performance status ≤ 2 (Karnofsky $\geq 60\%$, see Appendix A).

3.1.6 Diagnostic Imaging Baseline mammography prior to surgery is required. For patients with lymphatic involvement Computed Tomography (CT) scan of the chest, CT of the abdomen, and bone scan and/or Positron Emission Tomography (PET)/CT scan are required prior to delivery of chemotherapy. For most patients, this will be months prior to radiation. For patients with low burden nodal disease only mammography prior to surgery will be required.

3.1.7 Because radiation is known to be teratogenic, women of child-bearing potential and men must agree to use adequate contraception (hormonal or barrier method of birth control; abstinence) prior to study entry and for the duration of study participation. Should a woman become pregnant or suspect she is pregnant while participating in this study, she should inform her treating physician immediately.

3.1.8 Ability of the patient or the patient's legal guardian to understand and the willingness to sign a written informed consent document.

3.2 Exclusion Criteria

Participants who exhibit any of the following conditions at screening will not be eligible for admission into the study.

3.2.1 Patients will be ineligible if any prior therapeutic radiation therapy > 200 cGy has been delivered to the target volume.

CONFIDENTIAL

This document is confidential. Do not disclose or use except as authorized.

- 3.2.2 Patients will be ineligible if surgery and chemotherapy was completed ≥ 20 weeks from the planned start date of radiation therapy or if the patient is referred for radiation therapy after a relapse of prior ipsilateral breast cancer. Surgery can exceed 20 weeks if the patient undergoes chemotherapy following surgery.
- 3.2.3 Individuals with a history of a different malignancy are ineligible except for the following circumstances. Individuals with a history of other malignancies are eligible if they have been disease-free for at least 5 years and are deemed by the investigator to be at low risk for recurrence of that malignancy. Individuals with the following cancers are eligible if diagnosed and treated within the past 5 years: cervical cancer *in situ*, and basal cell or squamous cell carcinoma of the skin.
- 3.2.4 Pregnant females are excluded. Female subjects of childbearing potential must indicate to their physician that there is not a possibility of being pregnant at the time of enrollment or have a negative pregnancy test prior to initiation of radiation therapy.
- 3.2.5 Patients who received investigational chemotherapy prior to radiation therapy are excluded from this study.

3.3 Inclusion of Women, Minorities and Other Underrepresented Populations

We do not expect the inclusion and exclusion criteria to either over or under-represent minorities, or underrepresented populations. This protocol does not exclude males, but will enroll primarily females as breast cancer occurs predominantly in women.

4. REGISTRATION PROCEDURES

4.1 General Guidelines for DF/HCC and DF/PCC Institutions

Institutions will register eligible participants with the DF/HCC Quality Assurance Office for Clinical Trials (QACT) central registration system. Registration must occur prior to the initiation of therapy. Any participant not registered to the protocol before treatment begins will be considered ineligible and registration will be denied.

A member of the study team will confirm eligibility criteria and complete the protocol-specific eligibility checklist.

Following registration, participants may begin protocol treatment. Issues that would cause treatment delays should be discussed with the Principal Investigator. If a participant does not receive protocol therapy following registration, the participant's

CONFIDENTIAL

This document is confidential. Do not disclose or use except as authorized.

protocol status must be changed. Notify the QACT Registrar of participant status changes as soon as possible.

4.2 Registration Process for DF/HCC and DF/PCC Institutions

The QACT registration staff is accessible on Monday through Friday, from 8:00 AM to 5:00 PM Eastern Standard Time. If a participant must be registered during off-hours or holidays, call the QACT registration line at [REDACTED] and follow the instructions for registering participants after hours.

The registration procedures are as follows:

1. Obtain written informed consent from the participant prior to the performance of any study related procedures or assessments.
2. Complete the protocol-specific eligibility checklist using the eligibility assessment documented in the participant's medical/research record. **To be eligible for registration to the study, the participant must meet each inclusion and exclusion criteria listed on the eligibility checklist.**

Reminder: Confirm eligibility for ancillary studies at the same time as eligibility for the treatment study. Registration to both treatment and ancillary studies will not be completed if eligibility requirements are not met for all studies.

3. Fax the eligibility checklist(s) and all pages of the consent form(s) to the QACT at [REDACTED]

Exception: DF/PCC Affiliate sites must fax the entire signed consent form including HIPAA Privacy Authorization and the eligibility checklist to the Network Affiliate Office. The Network Affiliate Office will register the participant with the QACT.

4. The QACT Registrar will (a) validate eligibility, (b) register the participant on the study, and (c) randomize the participant when applicable.
5. The QACT Registrar will send an email confirmation of the registration and/or randomization to the person initiating the registration immediately following the registration and/or randomization.

5. TREATMENT PLAN

Treatment will be administered on an outpatient basis. Expected toxicities and potential risks of radiation are described in Section 6 (Expected Toxicities and Delays).

CONFIDENTIAL

This document is confidential. Do not disclose or use except as authorized.

5.1 Pre-treatment Criteria

- 5.1.1 Diagnostic Imaging: Patients with lymph node involvement must have a metastatic work up that includes Computed Tomography(CT) scan of the chest, abdomen and pelvis and bone scan or Positron Emission Tomography (PET)/CT scan.
- 5.1.2 Cardiology: Echocardiogram including Strain echocardiogram will be performed for all patients. Echocardiogram data will be collected prior to radiation therapy (or within first week of treatment), within 4 weeks after completion of radiation therapy, and 2 months after radiation therapy.
Echocardiography: Conventional two-dimensional (2D) and Doppler echocardiography will be obtained in standard views. Tissue Doppler imaging will be acquired using standard views. Imaging parameters will be optimized and the frame rate will be set greater than 150 frames/sec for acquisition of tissue Doppler imaging. Echocardiographic loops of at least 3 beats will be recorded. Echocardiograms will be read in the conventional manner and reported in the subject's medical record. TDI-derived parameters, such as myocardial velocities, strain, strain rate and torsion, will be analyzed offline using customized computer software (EchoPac, GE Healthcare, Milwaukee, WI).
- 5.1.3 Pathological review of surgical specimen at the Massachusetts General Hospital or other DF/HCC institution.
- 5.1.4 Complete History and Physical Examination
- 5.1.5 CBC with differential. TSH at baseline. Biomarkers will be obtained with baseline routine labs and in follow with routine labs at 2 additional follow up visits (at 4 weeks after radiation therapy and 2 months after radiation therapy): Approximately 5 cc of blood will be taken for each measurement of BNP and NTproBNP, and 5 cc of blood for ultrasensitive troponin. Blood will be spun at 3000 rpms for 10 minutes, the plasma aliquotted into daughter tubes and stored at -80. BNP levels will be measured with a twosite dual-monoclonal immunochemiluminescent assay (ADVIA Centaur® BNP, Bayer Diagnostics, Tarrytown, NY) using the ADVIA Centaur immunoassay system. NT-proBNP levels will be measured with an electrochemiluminescence sandwich immunoassay (Elecsys® ProBNP, Roche Diagnostics Inc, Indianapolis, IN) using the Roche 2010 system. For non acutely dyspnic subjects aged <75 years of age, the upper limit of normal is considered 125 pg/ml (manufacturers recommendations). Troponin I will be measured using a new generation

CONFIDENTIAL

This document is confidential. Do not disclose or use except as authorized.

technique that has shown increased sensitivity compared to routine measurements (Architect STAT troponin assay, Abbot Diagnostics).

5.1.6 Photography: (optional) to objectively track cosmetic outcome.

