1.3 Secondary Objectives

1.3.1 The endpoints in these objectives are descriptive and will form the basis for designing future studies. The Common Terminology Criteria for Adverse Events (CTCAE) version 4 will be used for grading toxicities.

- To evaluate the rate and severity of acute skin toxicity
- To evaluate the rate and severity of radiation pneumonitis, a sub-acute toxicity
- To evaluate the rate and severity of late skin toxicity
- To evaluate cosmetic outcome and patient satisfaction with cosmetic outcome

CONFIDENTIAL

This document is confidential. Do not disclose or use except as authorized.

- To evaluate acute and late toxicity of breast reconstruction following proton radiation
- To evaluate the need for unplanned additional surgery for breast reconstruction
- To evaluate early signs of cardiac effects from radiation therapy using Strain Echocardiogram

1.3.2 To describe the 5 year progression free survival rate of patients with breast cancer treated with proton radiation.

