cardiac events.²⁷ Doses of 25 Gy have been shown to induce temporary perfusion defects and ≥ 5 -6% of the heart receiving ≥ 25 -27 Gy has been accepted by some to define “unfavorable cardiac anatomy” based on correlation of this heart volume to the Stockholm trial for patients with left sided tumors that showed a high rate of cardiac morbidity and mortality.^{15, 21-22, 28-29} There is emerging data that doses to specific parts of the heart, such as the coronary arteries, may be more important in predicting cardiac outcomes.³⁰ Strain echocardiogram has recently shown promise as an accurate and relatively inexpensive study to determine myocardial abnormalities in the left ventricle for doses > 3 Gy immediately post radiation and at 2 months following radiation.³¹ Control patients receiving right sided radiation did not show any changes on post radiation studies. Pericarditis is a very rare toxicity, occurring in $<1\%$ of patients, but may lead to hospitalization.³² In addition, the increased use of cardiotoxic chemotherapy over the past several years adds yet another confounding factor to determining the effect of radiation therapy on cardiac outcomes. Doxorubicin and Herceptin, particularly when used in combination, are known to increase the risk of cardiac disease.³³⁻³⁴ These agents were not included in the chemotherapeutic regimens used in the aforementioned trials. Currently, Doxorubicin and Herceptin are both included in standard chemotherapeutic regimens and are often administered in combination.³⁵ It is not fully known how radiation therapy in the setting of these agents will affect cardiovascular outcomes. Maximal cardiac sparing achieved through proton therapy has the potential to decrease this risk by decreasing mean heart dose as well as volume receiving 40 Gy and 25 Gy (Figure 2 & 3).

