7. STUDY CALENDAR

Baseline evaluations are to be conducted within 6-weeks prior to start of protocol therapy. Scans must be done ≤ 12 weeks prior to the start of chemotherapy if delivered or radiation therapy if no chemotherapy is delivered. In the event that the participant's clinical condition is deteriorating, laboratory evaluations should be repeated within 48 hours.

Tests and Observations	Pre-study	During Radiation	Follow Up (1)
Informed Consent and registration	X		
Pathology Review (DF/HCC)	X		
Medical History	X		
Physical Exam	X		X
Echocardiogram (2)	X		X(2)
Imaging	X (3)		As clinically indicated
Toxicity/AE Assessment		X weekly	X
Data Sheets			X (4)
Labs (5)	X		X
Optional Photography	X	X	X

Notes:

(1) Follow up schedule is at 4 weeks and 2 months, and 6 months after treatment, then at 12 months and annually to five years after treatment. Labs are only collected at the first two follow up visits (4 weeks and 2 months). Visit window for follow up is +/- 3 weeks for the 4week and 8 week follow up visits, then +/- 6months for the 6month and annual visits.

(2) Echocardiogram including Strain echocardiogram will be performed for all patients. Echocardiogram data will be collected prior to radiation therapy (or within first week of treatment), at 4 weeks after completion of radiation therapy, and 2 months after radiation therapy. Conventional two-dimensional (2D) and Doppler echocardiography will be obtained in standard views. Tissue Doppler imaging will be acquired using standard views. Imaging parameters will be optimized and the frame rate will be set greater than 150 frames/sec for acquisition of tissue Doppler imaging. Echocardiographic loops of at least 3 beats will be recorded. Echocardiograms will be read in the conventional manner and reported in the subject's medical record. TDI-derived parameters, such as myocardial velocities, strain, strain rate and torsion, will be analyzed offline using customized computer software (EchoPac, GE Healthcare, Milwaukee, WI).

(3) Diagnostic imaging required pre-study:

- Baseline mammography prior to surgery
- For patients with lymphatic involvement Computed Tomography (CT) scan of the chest, CT of the abdomen, and bone scan and/or Positron Emission Tomography (PET)/CT scan are required. For patients with low burden nodal disease, these scans are not required.

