(4) The Patient Evaluation form and the Physician Data Therapy forms will be considered optional with the intent to complete at all follow up study timepoints and missed forms will not be considered as constituting protocol deviations or violations.

(5) Standard clinical labs including CBC with differential; TSH at baseline; Biomarkers will be assessed only at the times of echocardiography. Approximately 5 cc of blood will be taken for each measurement of BNP and NTproBNP, and 5 cc of blood for ultrasensitive troponin. Blood will be spun at 3000 rpms for 10 minutes, the plasma will be aliquotted into daughter tubes and stored at -80. BNP levels will be measured with a twosite dual-monoclonal immunochemiluminescent assay (ADVIA Centaur® BNP, Bayer Diagnostics, Tarrytown, NY) using the ADVIA Centaur immunoassay system. NT-proBNP levels will be measured with an electrochemiluminescence

CONFIDENTIAL

This document is confidential. Do not disclose or use except as authorized.

sandwich immunoassay (Elecsys® ProBNP, Roche Diagnostics Inc, Indianapolis, IN) using the Roche 2010 system. For non acutely dyspnic subjects aged <75 years of age, the upper limit of normal is considered 125 pg/ml (manufacturers recommendations). Troponin I will be measured using a new generation technique that has shown increased sensitivity compared to routine measurements (Architect STAT troponin assay, Abbot Diagnostics). Labs will be performed in conjunction with routine labs obtained pre- and post- treatment only at 3 time points, prior to radiation therapy, 4 weeks after radiation therapy, and 2 months after radiation therapy.

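### The baseline strain echocardiogram may be taken during the first week of radiation, which could attenuate the pre/post cardiac change; the analysis has no rule for such baselines

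*Combined protocol and SAP*

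**What the plan says.** The allowance appears twice. Section 5.1.2, which sits under the pre-treatment criteria, permits the first echocardiogram "prior to radiation therapy (or within first week of treatment"). Section 7, note 2, repeats it: "Echocardiogram data will be collected prior to radiation therapy (or within first week of treatment), at 4 weeks after completion of radiation therapy", followed by a third study at 2 months.

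Other statements place the baseline before radiation:

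- The opening of Section 7: "Baseline evaluations are to be conducted within 6-weeks prior to start of protocol therapy".
- Section 7, note 5, on BNP, NT-proBNP and troponin: "Biomarkers will be assessed only at the times of echocardiography". The same note then fixes the draws "only at 3 time points, prior to radiation therapy, 4 weeks after radiation therapy, and 2 months after radiation therapy".
- Section 12.2.3 compares one pre-radiation and two post-radiation values by ANOVA, with linear contrasts for change over time.

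The data serve the secondary objective in Section 1.3.1: "To evaluate early signs of cardiac effects from radiation therapy using Strain Echocardiogram". Section 2.2 justifies the method by reporting that strain imaging showed "myocardial abnormalities in the left ventricle for doses > 3 Gy immediately post radiation" and again at 2 months.

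Section 12 does not ask for the number of fractions delivered before the baseline study. It does not flag on-treatment baselines and plans no sensitivity analysis for them.

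**The concern.** The trial has no concurrent control group, so the within-patient change from baseline carries the whole strain analysis. By the protocol's own rationale, strain imaging picks up early radiation effects that are still visible at 2 months. If part of such an effect exists when an on-treatment baseline is recorded, subtracting that baseline removes it, and the estimated change moves toward zero. Strain results that show little change would then be harder to interpret.

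The wording is also inconsistent. A patient whose baseline echocardiogram falls in week 1 cannot have the biomarkers drawn both at the time of that study and before radiation. The first-week allowance also does not fit the general rule that baseline evaluations precede therapy.

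**Working it through.** The documents give no sample size calculation, effect size, standard deviation or power for the strain endpoint, so there is no planned figure to reproduce. The check sets bounds on the possible attenuation.

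**Inputs from the documents.** Prescribed dose 45 to 50.4 Gy(RBE), typically five treatments a week (Section 5.2.4). Cohort size for precision 26 (Section 12.2.1). Left-ventricular changes reported above 3 Gy (Section 2.2).

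**Assumptions.** Fraction size is not stated; 1.8 to 2.0 Gy(RBE) is assumed. The share *q* of patients with an on-treatment baseline and the ventricular dose under protons are not given, so *q* is varied.

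**Step 1: share of the course delivered by the end of week 1**, *f* = 5 × fraction size / total dose.

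| Total, Gy(RBE) | Fraction, Gy(RBE) | After 5 fractions | *f* |
|---|---|---|---|
| 45 | 1.8 | 9.0 | 20.0% |
| 45 | 2.0 | 10.0 | 22.2% |
| 50.4 | 1.8 | 9.0 | 17.9% |
| 50.4 | 2.0 | 10.0 | 19.8% |

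If the effect is linear in dose and persists, an affected patient's change shrinks by 0 (no fractions yet) up to about 18-22% (all five delivered).

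**Step 2: cohort mean.** Observed change = true change × (1 − *q f*). With *f* = 20%:

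- *q* = 10%: 0.10 × 0.20 = 2%
- *q* = 25%: 0.25 × 0.20 = 5%
- *q* = 50%: 0.50 × 0.20 = 10% (9% to 11% over the range of *f*)

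These are upper limits, because every affected patient is given all five fractions. With three fractions on average, they fall to three fifths: about 1%, 3% and 6%.

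**Step 3: threshold reading.** If more than 3 Gy to the ventricular region is needed, week 1 reaches it only where that region's full-course dose exceeds 3 / *f*. That is 3 / 0.222 = 13.5 Gy to 3 / 0.179 = 16.8 Gy. Below that, the attenuation would be near zero.

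**Step 4: keep or exclude affected patients?** As an illustration, take a paired normal approximation with two-sided alpha 0.05 and an effect with 80% power at n = 26 (standardised change 2.80 / √26 = 0.55). Keeping everyone with *f* = 20% gives power Φ[2.80(1 − 0.20*q*) − 1.96]. Excluding affected patients gives Φ[2.80√(1 − *q*) − 1.96].

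| *q* | Keep all | Exclude affected |
|---|---|---|
| 10% | 78% | 76% |
| 30% | 75% | 65% |
| 50% | 71% | 51% |

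Even with all five fractions delivered in every affected patient, exclusion loses more power than it recovers.

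**The case against.** The strongest reply is that no bias has been shown. The evidence in Section 2.2 was gathered after treatment, and nothing in the documents demonstrates a strain change within the first week. Attenuation requires that patients use the allowance, that an effect exists by then, and that it persists in the same direction. Section 2.1 also expects protons to spare the heart almost entirely, which makes the near-zero case in Step 3 plausible. This stands, and it is why the point is that the allowance could attenuate the change.

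The allowance may also have a purpose. Section 12 says target accrual was adjusted partly for completeness of strain testing. A first-week study may rescue a baseline that would otherwise be missing, and a missing baseline removes the patient from the paired change altogether. This stands too, and it argues against an absolute ban or a restricted main analysis.

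The conflict with note 5 arises only for patients who use the exception, so it is a matter of wording. It still leaves the biomarker baseline undefined for them.

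The stakes are limited. Section 1.3.1 calls the secondary endpoints descriptive, and no decision rule uses strain. Section 12.2.3 permits exploratory fixed effects for treatment factors, but these cannot adjust for fractions delivered before baseline unless that number is recorded.

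**Conclusion.** The point holds as a low-cost improvement. Two sections allow an on-treatment value to serve as the pre-radiation measurement, other text in Section 7 places the baseline before radiation, and the analysis does not distinguish the two kinds of baseline. The possible attenuation is 0 to about 18-22% per affected patient and about 10% at most in the cohort mean if half are affected. That rests on the assumed fraction size, linearity in dose and a persistent effect. It may be near zero under a threshold.

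A reader might infer that the strain results are biased by about a fifth, or that the schedule favours a finding of cardiac sparing. The documents support neither reading. A fifth is the limit for a patient with all five fractions delivered, the number of such patients is unknown, and no section says that a null strain result will be taken to establish sparing. The feasibility decision in Section 12.1 does not depend on strain and is unaffected.

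**What to change.** - For patients still to be enrolled, obtain the baseline echocardiogram and biomarkers before the first fraction where feasible within the existing 6-week window. Keep a first-week study only as a documented exception, so that baselines are not lost.
- For all patients, including those already treated, record the fractions delivered before the baseline echocardiogram and report how many baselines were on-treatment. Treatment and study dates are enough for this.
- In Section 12.2.3, keep all patients in the main contrast and add a sensitivity analysis limited to true pre-radiation baselines.
- Reconcile Section 5.1.2 with the opening paragraph and notes 2 and 5 of Section 7 on what counts as baseline, for both the echocardiogram and the biomarkers.

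The cost is slightly tighter scheduling and one extra analysis on fewer patients, which will be less precise than the main one.
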